9.6 Analysis of Secondary Efficacy Endpoints

Changes in marrow cellularity pre and post treatment will be determined by a hematopathologist categorically (improvement in marrow cellularity or no improvement) and will be reported as a point estimate with 90% binomial confidence intervals.

Changes in methylcellulose colony forming assays pre and post treatment will be assessed. Mean changes will be estimated with Student's paired t-test for null hypothesis with binomial confidence intervals.

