Metformin (N,N-dimethylbiguanide) has been used widely for many decades and has a well-characterized side effect profile. Initially this drug was developed for type II diabetes and insulin resistance; however, there has been recent renewed interest in Metformin given its anti-oxidant effects and potential protective effects, as observational studies have demonstrated a decreased incidence of breast cancer, lung cancer, colorectal cancer, and hepatocellular carcinoma in patients treated with Metformin, possibly through AMP-kinase activation and mTOR inhibition (summarized in ¹⁰). Relevant to this study, Metformin has also demonstrated aldehyde scavenging capabilities. Recent preclinical models both in FA cell lines and in FA mice have demonstrated that Metformin improved the platelet count and ANC in FA mice and that this may be mediated by increasing the percentage of cells in quiescence and by improving DNA repair, as Metformin treated fibroblast cells had decreased numbers of spontaneous radials and breakage.¹¹

Based on these data, we propose a single institution, open-label, single arm pilot study of Metformin in patients with Fanconi Anemia and cytopenias with the primary endpoint of hematologic response. This study will also assess safety, tolerability, and the biologic effects of Metformin in patients with FA.

- ↑ Clinic visit, labs, and marrow evaluation
- ↑ Clinic visit, labs, and PK samples (when available); otherwise, phone call and local labs
- ↑ Local labs
- ↑ Phone call and drug diary review
- ★

TABLE OF CONTENTS

1. OBJECTIVES	5
1.1 Study Design	5
1.2 Primary Objective	5
1.3 Secondary Objectives	5
1.4 Exploratory Objectives	5
2. BACKGROUND	6
2.1 Fanconi Anemia	6
2.2 Metformin	6
2.3 Rationale for evaluation of Metformin in Fanconi Anemia	8
2.4 Rationale for planned correlative studies	9
3.5 Overall summary of rationale	10
3. PARTICIPANT SELECTION	11
3.1 Inclusion Criteria	11
3.2 Exclusion Criteria	12
4. ENROLLMENT PROCEDURES	13
4.1 General Guidelines	13
4.2 Evaluable Patients	13
5. TREATMENT PLAN	13
5.1 Treatment Regimen	13
5.2 Agent Administration	15
5.3 Study Visit Procedures	15
5.4 General Concomitant Medication and Support Care Guidelines	17
5.5 Criteria for Taking a Participant Off Protocol Therapy	18
5.6 Duration of Follow Up	19
5.7 Schedule of Assessments	19
6. HEMATOLOGIC RESPONSE CRITERIA	21
7. ADVERSE EVENTS: LIST AND REPORTING REQUIREMENTS	22
7.1 Adverse Event Management	23
7.2 Dose Modification	23

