1.3 Secondary Objectives

- 1.3.1 To evaluate the hemoglobin, RBC transfusion requirements, platelet count, and absolute neutrophil count.
- 1.3.2 To evaluate the hematopoiesis through evaluation of marrow cellularity and hematopoietic progenitor colony assays.
- 1.3.3 To evaluate the safety in Fanconi Anemia patients.
- 1.3.4 To describe the pharmacokinetics in Fanconi Anemia patients.
- 1.3.5 To describe the tolerability in this population at the target dose for 6 months duration.

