2.5 Overall summary of rationale

Since Fanconi Anemia is a rare disease, a small prospective pilot study was chosen as the study design. Although the small sample size and open-label single-treatment arm design of this study will not be able to definitively determine clinical benefit of Metformin treatment in this patient population, this study will provide additional information regarding safety, tolerability, and preliminary efficacy of Metformin in FA patients and may provide the basis for a larger controlled clinical trial.

As Metformin would be used as a chronic medicine if it improves hematopoiesis, it is necessary to assess safety and tolerability of this medicine over several months. As our goal is to improve the understanding of the mechanisms by which Metformin may improve hematopoiesis, biological correlative studies will be integrated into the clinical trial with blood and marrow collection and analysis and may lead to additional hypotheses, which can in turn become the bases for additional potential therapies in this patient population.

There is urgency to run this trial since Metformin is available for clinical use and could easily be given off-study, in which case safety and efficacy will remain unclear, and there is a high unmet medical need for safe and tolerable medical therapies for patients with FA and marrow failure as there are no established treatment options for marrow failure other than bone marrow transplantation, androgen therapy, or hematopoietic growth factor therapy. Metformin is anticipated to be safe and tolerable in this patient population given the prior published clinical experience using this medication in various patient population including pediatric patients with type I and II diabetes and obesity, and Metformin is currently being used in trials for advanced solid tumors. The doses tested in this trial are doses which have either been FDA approved (ages 10 years and older), or doses which have been previously tested and well tolerated (ages 6-10 years).

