5.7 Schedule of Assessments

Baseline disease assessments, such as bone marrow studies, must be performed within 28 days prior to starting study drug.

Study visits 2-5 should be within +/- 3 days of, visits 6-10 and 12 should be within +/- 7 days, and visit 11 should be performed within +/- 14 days of what is specified per protocol.

Visit Name	Screening									End of treatment	Follow up	
Visit number	1	2 ⁺	3	4	5	6	7	8	9	10	11	12

Day of cycle (+/-3 days unless otherwise indicated)	-28 to -1	1	8	15	2	29 (+/-7 days)	57 (+/-7 days)	85 (+/-7 days)	113 (+/-7 days)	141 (+/-7 days)	169 (+/-14 days)	197 (+/-7 days)
Obtain Informed Consent	X											
Demography	X											
Inclusion/exclusion criteria	X											
Relevant medical history/current medical conditions	X											
Diagnosis of Fanconi Anemia	X											
Prior therapies	X											
Concomitant medications	X											
Physical examination	X										X	
Lansky/Karnofsky Performance status	X										X	
Height	X										X	
Weight	X										X	
Vital signs	X										X	
Bloodwork	X					X	X	X	X	X	X	X
- Hematology (CBC with diff and retic)	X					X	X	X	X	X	X	X
- Chemistry (chem 10, LFTs)	X					X		X			X	
- Vitamin B12 level	X										X	
- G6PD	X											
- Blood glucose	X					X		X			X	
- Insulin level	X					X		X			X	
- Oral glucose tolerance test	X										X	
- IGFBP-1	X										X	
- Chromosomal breakage test	X										X	
- Iron studies (TIBC, serum iron, ferritin)	X										X	
- Aldehyde analyses	X										X	
- Hemoglobin electrophoresis	X										X	

Urinalysis (macroscopic)	X						X			X	
Serum or urine pregnancy test	X						X			X	
Drug dispensation		X									
Pharmacokinetic samples					X **						
Buccal swab sample for micronuclei assessment	X									X	
Bone marrow aspirate/biopsy	X									X	
- Aspirate for morphology	X									X	
- Biopsy	X									X	
- Karyotype	X									X	
- BMF/MDS FISH	X									X	
- Flow cytometry	X									X	
- CD34 HSPC cycling	X									X	
- Aldehyde analyses	X									X	
Drug diary/Drug administration							X				
Research team phone calls			X	X	X	X ***	X	X	X	X	X

+ Visit 2 is the day that the subject begins taking the study drug

** To be completed if study visit 6 occurs at BCH

*** To be completed if study visit 6 does not occur at BCH

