9.1.2 Endpoints

Primary endpoint:

The primary endpoint is the proportion of subjects with a hematologic response.

Secondary endpoints:

- Secondary hematologic endpoints will evaluate change from baseline in:
 - hemoglobin
 - red cell transfusion requirements
 - platelet count
 - absolute neutrophil count
 - marrow cellularity
 - methylcellulose colony forming assays
- Safety: the proportion of subjects with adverse events by grade.
- Tolerability: median number of dose interruptions, median number of discontinuations, and proportion of patients who are able to achieve maximum dose of Metformin.
- Pharmacokinetics: pharmacokinetic profile and exposure of Metformin

Exploratory endpoints:

Exploratory biomarkers will describe change from baseline in:

- aldehyde-mediated damage
- chromosomal breakage and radial formation in response to DEB/MMC exposure
- cell cycling in CD34+ hematopoietic stem/progenitor cells
- serum insulin, fasting glucose, and oral glucose tolerance
- micronuclei formation in buccal swab samples

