9.2 Sample Size, Accrual Rate and Study Duration

The total sample size is anticipated to be 24 patients. It is anticipated that without additional treatment, only 5% of patients would achieve a hematologic response. We would be interested in Metformin as a treatment in this patient population if the hematologic response rate is 20% or higher. The trial will be single arm, one-stage trial. The treatment will be considered promising if at least 3/22 subjects have a hematologic response. The probability of observing at least 3/22 responders is at least 0.84 assuming the true response is $\geq 20\%$ and is $< 10\%$ if the true response is $< 5\%$. It is anticipated that we will need 24 patients to accrue 22 evaluable patients. Evaluable patients are defined in section 4.2.

It is anticipated that an average of 1-2 patients will enroll each month on study and the study duration is anticipated to be approximately 2 years.

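### Marrow cellularity is analysed only as improved or not improved, with no cut-off; the paired change in percent cellularity should be the main analysis of this secondary endpoint

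*Combined protocol and SAP*

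**What the plan says.** Section 1.3 sets the secondary objective that this endpoint serves: "To evaluate the hematopoiesis through evaluation of marrow cellularity and hematopoietic progenitor colony assays". Section 9.1.2 introduces the list that contains marrow cellularity with "Secondary hematologic endpoints will evaluate change from baseline in".

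Section 9.6 then gives the analysis. A hematopathologist judges the pre/post change "categorically (improvement in marrow cellularity or no improvement", and the result "will be reported as a point estimate with 90% binomial confidence intervals". Nothing further is specified: no threshold, no category for worsening, no percent-cellularity summary, no reference rate and no denominator. Nothing is said about whether the reader knows which slide came first.

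The marrow is sampled twice, at baseline and at Visit 11 (Day 169). On the first sample, Section 5.7 says: "Baseline disease assessments, such as bone marrow studies, must be performed within 28 days prior to starting study drug".

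**The concern.** A proportion improved has meaning only against two things: what counts as improved, and how often that would happen with no drug effect. The plan supplies neither for cellularity. Biopsy sampling and reading variation will make some second marrows look fuller than the first, and how many depends on a threshold the reader of the report will not know.

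The plan handles comparable measures more fully. Section 6 gives numeric cut-offs for each blood lineage and requires a response to be sustained for 8 weeks. Section 9.2 gives the primary endpoint a no-treatment rate of 5%. Section 9.6 for the colony assays and Section 9.8 for the exploratory markers analyse paired changes. Of the pre/post marrow and laboratory measures in 9.6 and 9.8, cellularity alone is reduced to yes or no.

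At stake is what the pilot can pass on. Section 2.5 hopes that it may support a larger controlled trial. Planning such a trial on cellularity would need a mean change and its SD, and an undefined yes/no call gives neither.

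**Working it through.** **The plan's own figures.** None is stated for marrow cellularity. The nearest is the primary rule in Section 9.2, at least 3 responders among 22. Exact binomial gives P(X ≥ 3 | n = 22, p = 0.20) = 0.8455 (stated: at least 0.84) and P(X ≥ 3 | n = 22, p = 0.05) = 0.0948 (stated: below 10%). Both reproduce. The 5% reference is for hematologic response only: "It is anticipated that without additional treatment, only 5% of patients would achieve a hematologic response". It cannot be borrowed for cellularity.

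**Improved rate with no true change.** Assume that each cellularity value carries independent normal error (biopsy sampling plus reading) with SD s. The documents give no value for s, so take 5, 10 and 15 percentage points. The difference of two values has SD s√2. For a cut-off of k points, the expected improved rate is 1 − Φ(k / (s√2)).

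| Cut-off | s = 5 | s = 10 | s = 15 |
|---|---|---|---|
| any rise (k = 0, no ties) | 50% | 50% | 50% |
| over 10 points | 8% | 24% | 32% |
| over 20 points | 0.2% | 8% | 17% |

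For example, with s = 10 and k = 10: 10 / 14.14 = 0.707, and 1 − Φ(0.707) = 0.24.

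**What the interval can and cannot do.** Exact 90% (Clopper-Pearson) intervals, taking 22 pairs for illustration:
- 6/22 = 27%, CI 13% to 47%. This agrees with a no-change rate of 24%, lies above one of 8% and lies below one of 50%. The same result would look like noise, like a gain or like a shortfall, according to the cut-off.
- 11/22 = 50%, CI 31% to 69%. This is exactly what no effect gives if any rise counts.

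The interval covers sampling error in the proportion. It does not cover uncertainty about the definition.

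**Information lost by the split.** If changes are normal and split at zero, the asymptotic efficiency of the sign test relative to the t-test is 2/π = 0.637, so 22 pairs carry about 22 × 0.637 = 14.0 pairs' worth. As a small-sample check, take 18 pairs, a standardized change of 0.5 and a nominal two-sided 0.10 level. Power is 0.65 for the paired t-test and 0.50 for the sign test (13 or more of 18, one-sided size 0.048). A different cut-off gives a different loss.

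**Denominator.** The 22 in Section 9.2 are patients evaluable for hematologic response. Section 4.2 admits to that set anyone with one month of drug, and anyone who stops for drug-related reasons. The second marrow is scheduled only at Visit 11, and the documents do not say that patients who stop early will have it. The number of pairs may therefore be below 22.

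**The case against.** The strongest answer is that this is a descriptive secondary estimate in a pilot. No test or success rule uses it, and Section 2.5 says that the study "will not be able to definitively determine clinical benefit of Metformin treatment in this patient population". A proportion with an interval can be read as description once improvement is defined. That stands, and it limits the point to a better analysis of one secondary endpoint.

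Several stronger readings are tempting, and the documents do not support them:
- A reader might infer that the slides are read unmasked, because the protocol's introduction describes a "single institution, open-label, single arm pilot study of Metformin in patients with Fanconi Anemia and cytopenias". Open-label describes treatment. On the slide reading the plan is silent, so the accurate statement is that masking is not specified.
- A reader might call the result uninterpretable. That goes too far: what fails is its use as evidence of an effect while the cut-off is undefined.
- A reader might see Sections 9.1.2 and 9.6 as contradictory. They are not: 9.1.2 fixes no scale, and a categorical change is still a change from baseline.
- A reader might take 50% as the expected no-effect rate. It is the upper end: it needs any rise to count and no ties, and ties fall under no improvement.
- The efficiency figure compares two tests, and the plan tests neither. It also treats a bounded percentage as normal, so it only illustrates the loss.

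It is also fair to say that a mean paired change is no better controlled than a proportion. Natural course, or the selection of patients with cytopenias, could move it from zero without any drug effect.

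**Conclusion.** The point holds as an improvement to the analysis of one secondary endpoint. Followed exactly, Section 9.6 still leaves the proportion improved resting on an unstated threshold, drops the size of the change and does not separate stable from worsening marrow. With no true change, the expected proportion is 50% if any rise counts (no ties) and 8% to 32% for a rise over 10 points. These figures assume normal, independent reading errors with SD 5 to 15 points, which are not document values. The existence of the gap does not depend on them; only its size does.

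Nothing here affects the sample size, the power or the 3-of-22 rule for the primary endpoint.

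**What to change.** Amend Section 9.6 so that:
- percent cellularity is recorded from the Visit 1 and Visit 11 biopsies;
- the mean paired change with a 90% CI is the main analysis of this endpoint;
- the denominator is the number of patients with both marrows, and that number is reported;
- the improvement call is kept as supportive, with a numeric cut-off set before any pair is read and chosen with reading and sampling variation in mind;
- where practical, the same hematopathologist scores both slides of a pair, coded so that the visit is hidden. Otherwise, the plan should say that the read is not masked.

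Both biopsies are already scheduled, so no patient procedure is added. The cost is a few lines of SAP text, relabelling of at most 24 slide pairs and a small amount of pathology time. The baseline marrow will probably be read clinically before dosing, so coded scoring may need a repeat research read, and a reader who saw the slide earlier may not be fully naive. The report should describe the paired change as uncontrolled and not as proof of a drug effect.

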9.7 Analysis of Safety and Tolerability

Any patient that received at least one dose of drug would be eligible for the safety set. The proportion of patients with each toxicity overall and by grade will be reported along with 90%

confidence interval. This will be reported for the toxicities that are at least possibly related and regardless of attribution. The proportion of patients who required at least one dose reduction, who required at least one dose delay, who completed therapy and achieved the goal dose (diabetes/obesity-related dosing) of Metformin will be reported along with the 90% exact binomial confidence interval. The median number of dose reductions and dose delays will also be reported.

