3.1.3 Diagnosis requirement

3.1.3.1 Participants must have a clinical diagnosis of Fanconi Anemia.

3.1.3.2 Participants must have confirmed DEB/MMC testing to document diagnosis of Fanconi Anemia.

3.1.4 Patients must have at least one of the following cytopenias:

- Hemoglobin $<$ 10g/dL
- Platelets $<$ 100k/uL
- Absolute neutrophil count $<$ 1000/uL

3.1.5 Participants must have normal organ function as defined below:

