3.2 Exclusion Criteria

- 3.2.1 Patients must not have undergone prior bone marrow transplantation.
- 3.2.2 Patients must not have very severe aplastic anemia at the time of enrollment which would require bone marrow transplantation (as defined by at least 2 out of the following 3: ANC <200/uL, platelets <20k/uL, absolute reticulocyte count <40k/uL). If patients are not eligible for a transplant and otherwise meet the inclusion/exclusion criteria, then they may enroll in this trial.
- 3.2.3 Patients must not be taking any other concurrent medications to improve their hematopoiesis such as androgens or growth factors such as G-CSF, EPO, or TPO mimetics. If any of these prior therapies, including androgens, have been taken, the patient must wait 30 days before enrolling.
- 3.2.4 Pregnant participants will not be entered on this study given that the effects of Metformin on the developing human fetus are unknown.
- 3.2.5 Breastfeeding mothers are not eligible because there is an unknown but potential risk for adverse events in nursing infants secondary to treatment of the mother with Metformin.
- 3.2.6 Patients must not have a history of allergic reactions attributed to compounds of similar chemical or biologic composition to Metformin.
- 3.2.7 Patients must not have uncontrolled intercurrent illness including, but not limited to, ongoing or active infection, symptomatic congestive heart failure, unstable angina pectoris, cardiac arrhythmia, or psychiatric illness/social situations that would limit compliance with study requirements.
- 3.2.8 Patients must not have prior history of symptomatic hypoglycemia over the past year or hypoglycemia with glucose <50mg/dL on screening and baseline laboratory assessments.
- 3.2.9 Patients must not have type 1 diabetes mellitus.

- 3.2.10 Patients must abstain from alcohol as part of this study.
- 3.2.11 Patients must not have a diagnosis of myelodysplastic syndrome or leukemia, or other concurrent malignancy undergoing treatment.
- 3.2.12 Patients must not have vitamin B12 deficiency.
- 3.2.13 Patients must not have G6PD deficiency.

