6 HEMATOLOGIC RESPONSE CRITERIA

Hematologic improvement is based on modified MDS IWG criteria, which is listed below.²⁴
 Improvement in counts should be sustained for at least two months and demonstrated by at least 2 consecutive measurements to be considered a hematologic response

Hematologic improvement	Response Criteria (responses must be sustained over a minimum of 8 weeks in duration)		
Erythroid response (pretreatment, <10g/dL)	Hgb increase by $\geq 1.5\text{g/dL}$ for non-transfusion dependent patients	For patients who are transfusion dependent: Transfusion independence Only transfusions given for Hgb $\leq 8\text{g/dL}$ or for symptoms will be counted in the response evaluation	
Platelet response (pretreatment, <100k/uL)	If initially $<20\text{k/uL}$ to start, then must increase to	If initially $\geq 20\text{k/uL}$ to start, then must have an absolute	

	>20k/UL with an absolute increase of 100%	increase of >30k/UL
Neutrophil response (pretreatment <1000/uL)	If initially <500/uL to start, then must increase to >500/uL with an absolute increase of >250/uL	If initially ≥500/uL to start, then must have an absolute increase of >500/uL
Progression or relapse after HI*	At least one of the following: Decrease in ANC by >50% from baseline and absolute value <1000, platelet count decrease by >50% from baseline and absolute value <100k, reduction in Hgb by ≥1.5g/dL and absolute value <10g/dL, or doubling in transfusion requirement	

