7.1 Adverse Event Management

Toxicities will be assessed according to NCI’s CTCAE version 4.0.

Metformin is primarily associated with gastrointestinal side effects and if patients are not able to tolerate therapy based on these side effects, they will undergo a dose reduction. Management guidelines are listed below in the dose modification section 7.2. Metformin is rarely associated with lactic acidosis, in which case the drug will be discontinued and patients will receive appropriate clinical management.

Adverse events and toxicities will be captured both by planned laboratory studies at pre-specified timepoints (see study calendar) as well as by patient reporting. Patient interviews will be conducted weekly and drug diaries reviewed weekly during the initiation phase, and then monthly during the maintenance phase of treatment.

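### The by-grade safety table in Section 9.7 ignores pre-dose counts, so unchanged entry cytopenias and new worsening can be reported together

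*Combined protocol and SAP*

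**What the plan says.** All references are to the combined protocol and SAP.

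- **Entry.** Section 3.1.4: "Patients must have at least one of the following cytopenias" (hemoglobin below 10 g/dL, platelets below 100k/uL, or ANC below 1000/uL). Very low counts are provided for. Section 3.2.2 excludes very severe aplastic anemia but adds "If patients are not eligible for a transplant and otherwise meet the inclusion/exclusion criteria, then they may enroll in this trial". The neutrophil response rule in Section 6 has a branch for the lowest starting values: "If initially <500/uL to start, then must increase to >500/uL with an absolute increase of >250/uL".
- **Capture and grading.** Section 7.1 grades by CTCAE version 4.0 and states: "Adverse events and toxicities will be captured both by planned laboratory studies at pre-specified timepoints". Section 7.2 has a hematologic toxicity block, so low counts belong to the toxicity data.
- **Endpoint and table.** Section 9.1.2: "Safety: the proportion of subjects with adverse events by grade". Section 9.7: "The proportion of patients with each toxicity overall and by grade will be reported", with a 90% confidence interval, and then "This will be reported for the toxicities that are at least possibly related and regardless of attribution".
- **Design.** Section 9.2: "The trial will be single arm, one-stage trial".

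**The concern.** In a population selected for low counts, a scheduled CBC on treatment will often return a gradable value even if nothing has changed. If that value is entered as a toxicity, the row describes the disease at entry as well as any effect of the drug. With no comparator arm, there is no background rate against which to read it.

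Section 1.3.3 makes safety in Fanconi Anemia a stated objective, and Section 2.5 says the study may provide the basis for a larger controlled trial. In marrow failure, whether counts worsened on the drug is a central safety question, and the planned by-grade table does not isolate the answer.

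**Working it through.** **1. Is there a baseline rule anywhere that governs the table?** The text that might supply one:

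- Section 7 defines attribution, seriousness and expectedness. It does not define onset or worsening relative to the pre-dose state.
- Section 7.2 acts by grade. Its grade 4 hematologic row refers to the Section 5.5 worsening criteria only to decide discontinuation. It also gives instructions for grade 4 patients who do not meet those criteria, so the block covers low counts that have not worsened in that sense.
- Section 5.5 is relative to baseline, but it is a removal criterion and needs 8 weeks of sustained worsening.
- Section 6 defines progression or relapse relative to baseline. Section 9.5 plans only response rates, plus time to and duration of response among responders.
- Section 9.4 summarises baseline counts for the group, which cannot identify who worsened.
- Section 9.1.2 lists change from baseline in hemoglobin, platelets and ANC. Section 9.6 gives methods only for marrow cellularity and colony assays.

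None of these decides what Section 9.7 counts.

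**2. The plan's own decision figures.** These are exact binomial tails.

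| Rule | True rate 20% | True rate 5% | Plan states |
|---|---|---|---|
| At least 3 of 22 responders (9.2) | 0.846 | 0.095 | at least 0.84; below 10% |
| At least 3 of 24 grade IV events (9.3) | 0.885 | 0.116 | 0.89; 0.12 |

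All four reproduce. The first rule does not use toxicity grades. The second excludes hematologic events (Sections 8.2 and 9.3). Neither changes.

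**3. What one row of the table can show.** Take one lineage and one grade. Let m be the patients with that grade before Day 1 and unchanged, and w the patients who newly worsen to it. Assume that all 24 planned patients take at least one dose and that unchanged counts are entered. The row then prints (m + w)/24.

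The documents do not give m. Entry-grade distributions are absent and the CTCAE cut-offs are not printed, so m is an assumption with range 0 to 24. The intervals are 90% exact (Clopper-Pearson).

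| Assumed m, w | Row as planned | Worsening only |
|---|---|---|
| 12, 0 | 12/24 = 50.0% (31.9% to 68.1%) | 0/24 = 0% (0% to 11.7%) |
| 9, 3 | 12/24 = 50.0% (31.9% to 68.1%) | 3/24 = 12.5% (3.5% to 29.2%) |
| 0, 0 | 0/24 = 0% (0% to 11.7%) | 0/24 = 0% (0% to 11.7%) |
| 6, 0 | 6/24 = 25.0% (11.5% to 43.5%) | 0/24 = 0% (0% to 11.7%) |
| 24, 0 | 24/24 = 100% (88.3% to 100%) | 0/24 = 0% (0% to 11.7%) |

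The upper limit for 0/24 is 1 − 0.05^(1/24) = 0.117. The first two lines print the same row although three patients worsened in one and none in the other. The m = 24 line is only the end of the range: it would need every patient to hold the same lineage at the same grade, whereas Section 3.1.4 requires only one of three cytopenias.

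**4. A limit on the remedy.** Visits 6 to 11 give six on-treatment CBCs, against one pre-dose CBC. With no drug effect and seven exchangeable values, the lowest of six falls below the pre-dose value with probability 6/7 = 0.857. Only some of those falls cross a grade line. Exchangeability is itself an approximation, since patients are selected for low counts and may be transfused (Section 5.4.1.4).

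**The case against.** The strongest reply is that this is a reporting convention in one descriptive table of a pilot. Investigators may not record stable cytopenias as events. If they do, attributing them to Fanconi Anemia keeps them out of the at-least-possibly-related table. Change from baseline in counts is a listed secondary endpoint, removals under Section 5.5 are documented with reason and date, and Section 9.7 reports completion of therapy. The patient numbers above are chosen, not derived.

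Most of this stands and limits the point. Attribution does protect the related table, if unchanged counts are attributed that way. It gives no protection to the table that ignores attribution, and the plan nowhere tells investigators to leave stable cytopenias out.

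Three stronger readings are tempting, and the documents do not support them:

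- **That the trial report as a whole could not reveal worsening.** This is true of the by-grade table only. The count endpoints and Section 5.5 removals give other, partial information. The two example trials also differ at baseline (12 against 9 patients at that grade).
- **That the hematologic toxicity rates will be inflated by a known amount.** The value of m cannot be obtained from the documents, so the table above shows the mechanism and not an expected size.
- **That the grade 3 and 4 hematologic rows of Section 7.2 would block titration because of an entry cytopenia.** In the grade 4 row, maintaining the dose is the alternative to discontinuing, so not stopping is a natural reading. On schedule, patients aged 10 and over reach the target dose at the start of week 4 (Day 22), which is the first day of the Visit 6 window (Day 29 ± 7). No planned on-treatment CBC precedes it. The blocking reading needs both a slipped titration and a particular sense of one word.

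**Conclusion.** The concern holds, as a minor one, for the hematologic rows of the Section 9.7 table that ignores attribution. Followed as written, those rows can combine unchanged entry cytopenias with new worsening, so the table cannot show how many patients worsened on metformin. This rests on two things: the absence of any baseline rule in the safety text, and stable low counts from scheduled CBCs being entered as toxicities, which the plan permits but does not explicitly require. The size cannot be derived. No sample size, error rate or decision rule is affected. It is worth correcting because a clearly better tabulation is available from data already planned.

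**What to change.** Change Section 9.7 only, by adding:

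- For hemoglobin, platelets and ANC, tabulate pre-dose CTCAE grade (last CBC before the first dose) by worst on-treatment grade and by Visit 11 grade.
- Report as hematologic toxicity the proportion of patients whose grade worsened from pre-dose, with the 90% confidence interval.
- For patients already at grade 4 before Day 1, report worsening by the Section 5.5 criteria.

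Section 7.2 needs no change.

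**Cost.** Three sentences and no new data. The pre-dose CBC is already collected, and Section 4.1 has it repeated if it is more than 14 days old on Day 1.

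**Downsides.** Falls within a grade are not counted. They would appear only in the change-from-baseline endpoints, for which Section 9.6 still gives no method, or under Section 5.5 if large and sustained. For patients starting at grade 4, the 8-week requirement in Section 5.5 will miss short dips. Comparing the worst of six CBCs with one pre-dose CBC overstates worsening, so the Visit 11 column should be read alongside. A pre-dose CBC drawn soon after a transfusion could also make a later value look worse than it is.
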